Among obese women, the labor curves indicate longer overall duration (from 4 cm to 10 cm dilatation) and slower progression of the early first stage of labor (from 4-6 cm) after adjusting for confounders.⁵ Obese women have longer labors but are equally able to achieve adequate uterine contractions⁶ but obese nulliparas need more powerful contractions to reach the active stage of labour (> 6 cm cervical dilation) though this phenomenon does not exist in obese multiparas⁷. Not only is reaching the active stage of labour more difficult among the obese, failed induction of labour is also more common.⁷ BMI was higher in women with labour dystocia (inadequate labour progress) and pre-pregnancy BMI also had a strong association with dystocia risk such that for BMI increment of 1 kg/m², the caesarean section risk increased by a relative 10%.⁸

Oxytocin is a peptide hormone (a self-produced natural agent) that plays a key role in regulating the female reproductive system, including during labor and lactation. Oxytocin can also be administered as a medication to initiate (induce labour) or augment uterine contractions (to overcome inadequate labour progress). Oxytocin has a plasma half-life of 6 minutes 53 seconds in female serum.^{9, 10}

A 2024 meta-analysis of high and low oxytocin dose regimen analysed 21 studies (a total of 14.834 patients including from 18 RCTs) reports that "no statistical differences were found in cesarean delivery, neonatal mortality, postpartum hemorrhage and vaginal instrumentation rate. However, uterine tachysystole (frequent contractions) incidence was significantly higher with high-dose oxytocin".¹¹ A 2024 expert review comments "randomized trials demonstrated that active management of labor and high-dose oxytocin regimens can shorten the length of labor and reduce the incidence of clinical chorioamnionitis. The safety of high-dose oxytocin regimens is also supported by no associated differences in fetal heart rate abnormalities,

postpartum hemorrhage, low Apgar scores, neonatal intensive care unit admissions, and umbilical artery acidemia. Most studies reported no differences in the cesarean delivery rates with active management of labor or high-dose oxytocin regimens, thereby further validating its safety."¹² A 2013 expert review states "high-dose infusions of oxytocin may shorten the duration of labor by up to 2 hours".¹³ A 2020 review by the Agency for Healthcare Research and Quality (US) on comparative effectiveness of interventions for labor dystocia reports that highdose oxytocin is associated with a lower cesarean delivery rate (moderate strength of evidence) with no difference in maternal hemorrhage (low strength of evidence) in nulliparous women.¹⁴ A 2013 Cochrane systematic review and meta-analysis reports a higher dose of oxytocin was associated with a significant reduction in length of labour (mean reduction of 3.5 hours, reported from one trial¹⁵) and no significant differences for instrumental vaginal birth, epidural analgesia, hyperstimulation, postpartum haemorrhage, chorioamnionitis or women's perceptions of experiences.¹⁶

The above findings indicate that the undesirable increase in tachysystole¹¹ with high dose oxytocin does not translate to adverse maternal outcome (e.g., postpartum haemorrhage^{11-14, 16} epidural analgesia¹⁶ or women's perceptions of experiences¹⁶) or adverse neonatal outcome (e.g., fetal heart rate abnormalities, low Apgar scores, neonatal intensive care unit admissions, umbilical artery acidemia, neonatal mortality)^{11, 12}. On the other hand, chorioamnionitis¹², caesarean birth¹⁴ and the length of labour^{12, 13, 15, 16} could be decreased with high dose oxytocin.

A 2023 secondary analysis of data from a multicentre USA trial of 1003 participants focused on the impact of high oxytocin dosing where the maximum oxytocin rates used ranged from 2 to 90 mIU/min finds no significant differences in maternal or perinatal adverse outcomes with higher oxytocin dose concluding that oxytocin dosing should be individualized to each patient and not be based on arbitrary limits.¹⁷

"Oxytocin infusion protocols for labor induction and augmentation differ widely, in part, because a predictable dose response for uterine contractions or labor does not exist."¹³ A 2020 survey performed in 12 European countries shows starting rates of 1 to 15 mIU/min, maximal infusion rates of 15 to 60 mIU/min, different intervals for infusion rate variation and the predicted total oxytocin infused during 8 hours ranging from 2.38 to 27.00 IU demonstrating the substantial diversity in European national practice.¹⁸

Physiological changes caused by obesity can impact all the four principal pharmacokinetic phases of absorption, distribution, metabolism and elimination¹⁹ warranting the consideration of obesity in drug dosing regimens. A 2024 trial of misoprostol induction of labour in obese patients reports a reduction in labor time when comparing high and standard doses without maternal or neonatal detriment²⁰ supporting the proposition of benefit with higher doses in obese parturients in the management of labour.

The overall impression from these data suggest safety and potential benefit from higher dose oxytocin for labour dystocia. Plausibly in obese nulliparas there is an even stronger case for overall benefit, warranting responsible further investigation.

We propose a trial on two oxytocin dosing regimens for labour dystocia in obese parturients. Infusion solutions will be made with 15 IU (experimental) or 10 IU (control, standard dose) in a

container of 500 ml Hartmann's. The experimental regimen will start at a higher dose (3 vs 2 mlU/min – European national starting rates of 1 to 15 mlU/min¹⁸) and be bounded to a higher maximum dose limit (48 vs 32 mlU/min - European national maximal rates of 15 to 60 mlU/min¹⁸ and up to 90 mlU/min used in a 2024 large multicentre USA-based trial¹⁷) compared to our standard regimen. In both arms, consideration for rate increment will be at every 30 minutes in the escalation phase to be titrated to uterine contraction frequency and strength as longstanding UMMC practice protocol of doubling the infusion rate as needed (from 6 ml hr to 12 ml/hr to 24 ml/hr hour to 48 ml/hr to 96 ml/hr). The infusion rate will be increased stepwise until the 'ideal' 3-to-4 every 10 minutes of moderate-to-strong contractions is achieved. Thereafter the infusion rate will be maintained to birth provided that the 'ideal' contraction response is sustained. Subsequently, any deviation from this ideal response may require infusion rate adjustments which will be at the full discretion of care providers guided by the principle of their usual practice in the best interest of the patient.

OBJECTIVES & EXPECTED OUTCOMES

PRIMARY OBJECTIVE:

A shortened interval from initiation of titrated oxytocin to birth (faster labour)

PRIMARY OUTCOME

We hypothesise that obese patients (BMI \geq 27.5- Asian criteria) administered with a higher concentration solution regimen, hence higher initial and maximum allowable dose of oxytocin in augmentation of labour will have their birth hastened in comparison with our current standard regimen

SECONDARY OBJECTIVE:

Secondary use, performance and safety outcomes partly derived from the core outcome set for reporting trials on induction of labour: CROWN21

- Maternal secondary outcomes
- 1) Maximum oxytocin infusion rate used
- 2) Duration of oxytocin infusion
- 3) Total volume infused (to derive total oxytocin dose infused)
- 4) Cardiotocographic abnormality (through first stage of labour)-assessed by a blinded assessor
- a) Tachysystole (contractions ≥ 6 in 10 minutes)
- b) Hypertonus (sustained contraction ≥ 2 minutes)
- c) Hyperstimulation syndrome (tachysystole and/or hypertonus with concurrent fetal deceleration [defined as decrease in fetal heart rate of \geq 15 bpm from baseline for \geq 15 second]) 5) Number of doses of tocolytic given if any
- 5) Number of doses of tocolytic given if any
- 6) Mode of delivery
- a) spontaneous
- b) vacuum
- c) forceps
- d) caesarean section
- 7) Indication for caesarean section
- 8) Indication for instrumental vaginal delivery

- 9) Maternal satisfaction with the birth process (11-point 0-10 NRS numerical rating scale)
- 10) Blood loss during delivery
- 11) Third- or fourth-degree tear
- 12) Maternal infection
- 13) Intrapartum therapeutic antibiotics (excluding prophylactic antibiotics)
- 14) Epidural in labour
- 15) Length of hospital stay
- 16) ICU admission
- 17) Cardiorespiratory arrest
- 18) Needing hysterectomy
 - Neonatal outcomes
- 1) Apgar score at 1 and 5 minutes
- 2) NICU admission
- 3) Cord pH
- 4) Neonatal sepsis
- 5) Birth weight
- 6) Birth trauma
- 7) Hypoxic ischaemic encephalopathy/need for therapeutic hypothermia

METHODOLOGY

Study design

Single centre, parallel group, conveniently sampled, double blinded, randomized controlled trial.

Population of Study:

Term obese (BMI \geq 27.5 kg/m2) parturient with singleton pregnancies requiring oxytocin augmentation for labour dystocia

Inclusion criteria

- 1. BMI ≥27.5 kg/m²
- 2. Spontaneous labour (contraction >2:10 minutes and cervical dilatation \geq 3cm)
- 3. Inadequate progress as clinically determined
- 4. Nulliparous (no previous pregnancy ≥22 weeks)
- 5. Term ≥37 weeks
- 6. Age 18-45 years old
- 7. Membranes ruptured (including prelabour rupture of membranes)
- 8. Singleton pregnancy
- 9. Cephalic presentation
- 10. Reassuring fetal heart rate tracing at initiation of oxytocin infusion

Exclusion criteria

- 1. Induced labour (prior Foley, prostaglandin or oxytocin)
- 2. Previous uterine scar (caesarean/myomectomy/perforation)
- 3. Known major fetal anomaly
- 4. Fetal weight clinically estimated to be $\leq 2 \text{ kg } \& \geq 4 \text{ kg}$ and confirmed by ultrasound

Recruitment

Potentially eligible nulliparas in the antenatal or labour ward in spontaneous labour with the decision made to augment labour with oxytocin will be screened with the Eligibility Assessment Form [EAF]. Screened patients will be verbally engaged regarding study participation and the Participant Information Sheet [PIS] with be given. Queries about the study will be invited and answered by the recruiting care provider. Informed written consent will be required of all participants.

Randomisation

The randomisation sequence will be generated an investigator not involved in the recruiting or care process in random blocks of 4 or 8 using an online randomiser (https://www.sealedenvelope.com/simple-randomiser/v1/lists).

Allocated intervention oxytocin-Hartmann solution will be enclosed in numbered boxes. The lowest numbered box still available will be allocated for the latest recruit. A co-numbered sealed opaque envelope with external writing of "UNBLINDING INFORMATION: Open Only If Necessary" and containing a card with "Study Number xxx, OXYTOCIN STUDY DRUG 10 IU (Standard dose) in 500 ml Hartmann" or "Study Number xxx, OXYTOCIN STUDY DRUG 15 IU (High dose) in 500 ml Hartmann" will be pasted to the box.

The reason for the necessary opening of this envelope for clinically necessary unblinding will be recorded. Contents of the numbered boxes unused will be discarded and replaced every 24 hours.

The numbered trial boxes containing the trial oxytocin solutions will be stored in our airconditioned delivery suite with ambient temperature set at 22-24 0C25.

Interventions

The interventions are titrated oxytocin infusions using

a) Higher starting dose and higher maximum dose

Starting dose (3 mIU/min) increasing as needed to a maximum of 48 mIU/min) (infusion rate of 6 ml/hr to a maximum rate of 96 ml/hr of 15 IU oxytocin in 500 ml Hartmann's solution)

OR

b) Standard starting dose and standard maximum dose

a standard starting dose (2 mIU/min) increasing as needed to a maximum of 32mIU/min) (infusion rate of 6 ml/hr to a maximum rate of 96 ml/hr of 10 IU oxytocin in 500 ml Hartmann's solution)

An electric pump will be used for oxytocin infusion. Total volume infused, duration of infusion and maximum rate of infusion will be recorded.

In both arms, the regimen for titrating the oxytocin infusion rate will be the usual care regimen of doubling the infusion rate (from 6 ml hr to 12 ml/hr to 24 ml/hr hour to 48 ml/hr to 96 ml/hr as needed) every 30 minutes until 3-4 moderate-to-strong contractions is achieved following which the infusion rate will be maintained until delivery if there are no interim events. Tocolysis use will be recorded.

In the event of cardiotocograph abnormalities or other clinical concern, the care provider has full discretion to pause, restart and discontinue the oxytocin infusion.

Blinding

Oxytocin-Hartmann infusion packs (10 or 15 IU oxytocin in 500 ml Hartmann's solution) will be made daily and discarded if unused after 24 hours by an investigator not involved in recruitment. Three packs of allocated strength oxytocin solution will be labelled with a number matched to the number on the linked randomisation envelope, OXYTOCIN STUDY DRUG (Pack 1, Pack 2 or Pack 3). The participant's hospital label will also be stuck to these three number and Pack list-ordered OXYTOCIN STUDY DRUG packs once the envelope assigned. The three OXYTOCIN STUDY DRUG packs (total volume 1500 ml) is sufficient for more than 16 hours of oxytocin infusion even after reaching and sustaining the maximum rate of 96 ml/hr.

Uterine overstimulation	Suggested Remedy
1) Tachysystole	a) Halve the oxytocin infusion rate
(contractions ≥6 in 10 minutes without fetal heart rate abnormality)	b) If inadequate response after 10 minutes, pause infusionc) If inadequate response after 10 minutes,
 Hypertonus (sustained contraction ≥2 minutes without heart rate abnormality) 	administer 500 mcg terbutaline subcutaneously a) Pause the oxytocin infusion if persistent b) If inadequate response after 2 minutes, administer 500 mcg terbutaline subcutaneously c) If inadequate response after another 2 minutes, administer another 500 mcg terbutaline subcutaneously
3) Hyperstimulation syndrome (tachysystole and/or hypertonus with concurrent fetal deceleration decrease in fetal heart rate of ≥15 bpm from baseline for ≥15 second)	 a) Pause infusion, consider concomitantly, administer 500 mcg terbutaline subcutaneously b) If inadequate response after 2 minutes, administer another 500 mcg terbutaline subcutaneously c) Consider caesarean delivery if cardiotocograph deteriorates from suspicious to pathological

Suggested rescue measure for uterine overstimulation

Care providers shall pause, restart (at appropriate dose) and discontinue the oxytocin infusion according to best judgment.

Intrapartum care, delivery and postnatal care.

Continuous electronic fetal monitoring with the cardiotocogram will be instituted until birth. Monitoring of maternal pulse, blood pressure, temperature, urinalysis, vaginal assessment for progress, etc. will be carried out at the usual intensity, Interim events detected will be responded to according to standard practice at the complete discretion of care providers. Decisions on timing and mode of delivery will be made as normal. Similarly, delivery and postnatal care will be managed along the same principles.

Stopping rules

- Study stopping rule
- 1) The study will be paused in the event of occurrence of any major harms of

a) Neonatal hypoxic ischaemic-encephalopathy requiring cooling therapy due to uterine hyperstimulation syndrome

b) Maternal convulsions due to water-intoxication

and reported to competent oversight by the department safety monitoring committee in first instance. The study shall not resume until subsequently authorise to do so.

• Participant stopping rule

1) If there is a clinical need, the concentration of oxytocin in the infusion solution can be immediately revealed by opening the unblinding sealed opaque envelope that contained the required information

2) If there is further clinical need, the allocated study infusion pack can be stopped and replaced by oxytocin infusion solution of a different strength at the discretion of the care provider

Interim analysis

The primary outcome is the interval from start of oxytocin augmentation to birth and the study is powered to this clinically relevant but not critical outcome. The target sample size is not large at 126. In view of the aforementioned considerations, an interim analysis is not planned.

Sample size

A 2023 nulliparous labour induction trial from UMMC reports that the interval from start of oxytocin infusion start to birth was 7.6±3.7 vs 8.2±3.3 across arms.26

A 2013 expert review states "high-dose infusions of oxytocin may shorten the duration of labor by up to 2 hours".13 A 2013 Cochrane systematic review and meta-analysis reports that a higher dose of oxytocin was associated with a significant reduction in length of labour reported from one trial15 (mean difference (MD) -3.50 hours; 95% confidence interval (CI) -6.38 to -0.62; one trial, 40 women).16

Applying a conservative standard deviation of 4 hours (vs. 3,3-3,7 hours)26 and a mean difference of 2 hours (213-3.516 hours), utilising online calculator OpenEpi (https://www.openepi.com/SampleSize/SSMean.htm) and additionally inputting alpha 0.05, power 80% and 1 to 1 ratio, and by t-test analysis, a total of 126 participants are needed for a powered study. We plan to recruit 126 patients (63 in each arm).

Data Analysis

Statistical software package SPSS (Version 27, IBM, SPSS Statistics) will be used. The Student t-test will be used for analysis of continuous data with normal distribution, the Mann-Whitney U test for non-normally distributed or ordinal data and Chi-square test for nominal data (Fisher exact test was used if the expected cell number <5 in \geq 20% of cells evaluated). 2-sided p values will reported and the level of significance is set at p<0.05. Analysis will be on intention-to-treat basis.

Only the investigators. Anonymized (where individuals cannot be identified) trial data may be released to other researchers in the future as permitted by the Ethics committee.

How long will the data be kept?

The data will be kept for a minimum of 10 years.

REFERENCES

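### Study-pause trigger (a) covers a cooled newborn but not a stillbirth or an uncooled neonatal death from the same cause, and death is not a named neonatal outcome

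*Protocol*

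**What the plan says.** The study stopping rule (Protocol, Stopping rules) opens with "The study will be paused in the event of occurrence of any major harms of" and then lists two items: (a) "Neonatal hypoxic ischaemic-encephalopathy requiring cooling therapy due to uterine hyperstimulation syndrome" and (b) "Maternal convulsions due to water-intoxication". It has no wording that extends the list to other serious events. When a trigger is met, the event goes first to the department safety monitoring committee, and the study stays paused until it is authorised to resume.

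The next section, Interim analysis, says that none is planned. Its reasons are the nature of the primary outcome and the modest target of 126 participants.

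The neonatal outcomes (Protocol, Secondary objective) are seven: Apgar score, NICU admission, cord pH, sepsis, birth weight, birth trauma, and "Hypoxic ischaemic encephalopathy/need for therapeutic hypothermia". Stillbirth and neonatal death are not named.

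The background, before the objectives, argues that the extra tachysystole seen with high-dose oxytocin does not lead to neonatal harm. Its list of those harms ends with "umbilical artery acidemia, neonatal mortality".

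**The concern.** A pause rule should rank outcomes on one causal pathway consistently: if a given injury stops recruitment, a worse result of the same mechanism should stop it too. Trigger (a) does not do this. It requires a live-born baby, a diagnosis of encephalopathy and a need for cooling. A baby who dies in labour meets none of these, and a newborn who dies without cooling does not meet the cooling condition.

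The stakes are participant safety and the usefulness of the safety report. The experimental regimen raises the maximum rate from 32 to 48 mIU/min, and the protocol itself acknowledges more tachysystole with high doses. Harm through hyperstimulation is therefore the foreseeable risk, and the rule is evidently written with it in mind. If the gravest form of that harm occurred, staff following the text literally would have no instruction to pause, and the final report would have no named outcome under which to show it by arm.

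**Working it through.** The point is textual, so the check sets four possible results of hyperstimulation against the pause rule and the outcome list.

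| Result of hyperstimulation | Trigger (a) met as worded? | Neonatal outcome that records it |
|---|---|---|
| Encephalopathy, cooled, survives | Yes | Item 7, directly |
| Encephalopathy, cooled, later dies | Yes, through the cooling | Item 7; the death itself is not named |
| Neonatal death without cooling | No | Item 7 if encephalopathy was diagnosed; otherwise Apgar, cord pH or NICU admission; the death itself is not named |
| Intrapartum stillbirth | No | Apgar (0 if scored) or cord pH if taken; the death itself is not named |

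Three observations follow.

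1. The first row pauses the study. The last two rows are worse results of the same mechanism and do not.
2. Trigger (b) is maternal and cannot fill the gap. The participant stopping rule cannot either: it deals with unblinding and replacing one woman's infusion, not with the study.
3. Trigger (a) and neonatal item 7 match each other, so rule and outcome list agree on encephalopathy with cooling. They also share one omission: neither names death.

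The plan's sample size is unaffected. With SD 4 hours, difference 2 hours, two-sided alpha 0.05 and power 80%, n per arm = 2 × (1.960 + 0.842)² × 4² / 2² = 2 × 7.85 × 4 = 62.8, rounded up to 63, or 126 in total. This reproduces the stated figure, and nothing in the present point enters the formula.

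**The case against.** The strongest reply is that the gap is narrow and would be closed in practice. A baby who is cooled and later dies has already paused the study. A generous reader might also count a baby who qualified for cooling but died before it began. A safety monitoring committee exists, and general adverse-event reporting may stand in pages that were not available. The event should be rare in term pregnancies with a reassuring tracing at entry and continuous monitoring.

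Much of this is fair, and it limits the point to deaths without cooling. It does not remove it. No reading of trigger (a) reaches a stillbirth. The committee appears only inside this rule and is given no wider trigger in the text shown. Both existing triggers are themselves severe harms of the kind one hopes never to see, so rarity is no reason to leave out the worst one.

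A reader might also infer more than the documents support:

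- *That a death would make the safety table look better.* This is not shown. The outcomes include "Apgar score at 1 and 5 minutes" and cord pH, and item 7 is worded so that encephalopathy can count without cooling. A severely affected baby would usually register as worse on these.
- *That maternal convulsion must be added to the maternal outcomes because it is a trigger.* That is a preference. The rule already requires the event to be reported, and an outcome list is not the case record form.
- *That the background contradicts the outcome list.* It cites mortality as a finding of other studies, and the protocol says that its outcomes are only partly taken from a core outcome set. The mismatch weakens the safety argument but breaks no commitment.
- *That this rule is the trial's only safety brake.* This can be said only of the text available.

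**Conclusion.** The point holds in this limited form. Trigger (a), in a closed list of two harms, does not cover intrapartum stillbirth or neonatal death without cooling due to hyperstimulation, although it covers the less severe case of a cooled survivor. Death is also not a named neonatal outcome. This is a defect in a rule that the protocol states, not a detail left to a later analysis plan.

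Its size is qualitative. The documents give no perinatal death rate, so no expected number of events can be derived and none is claimed. No estimate, power or sample-size figure changes. The conclusion assumes that the pause rule and outcome lists are complete as shown, and that no wider study-level trigger stands in pages that were not available. It is worth an amendment because the consequence of a single event would be serious and the change is small.

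**What to change.** Reconcile trigger (a) with the neonatal outcome list:

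- Word trigger (a) so that it also covers intrapartum or neonatal death attributed to uterine hyperstimulation.
- Require intrapartum and neonatal deaths in the trial to be reported to the department safety monitoring committee, and let the committee decide attribution. State whether recruitment is held while the cause is undecided; otherwise the trigger depends on a judgement that nobody has yet made.
- Add stillbirth/neonatal death as a named neonatal outcome, reported by arm.

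The cost is a short protocol amendment, one more data field and possibly one more committee review. The change concerns trial oversight and data capture only. It alters no dose, rescue measure or other clinical management.

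### The primary comparison leaves cervical dilatation at oxytocin start out of both randomisation and analysis, and so gives up precision that could be had almost free

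*Protocol*

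**What the plan says.** The primary outcome is the interval from the start of oxytocin augmentation to birth (Interim analysis; Primary objective).

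Data Analysis chooses the test by data type: "The Student t-test will be used for analysis of continuous data with normal distribution", Mann-Whitney U for non-normal or ordinal data, and chi-square or Fisher for nominal data. It names no covariate and no regression model.

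The Sample size section rests on the same t-test: "Applying a conservative standard deviation of 4 hours", "a mean difference of 2 hours", and "additionally inputting alpha 0.05, power 80% and 1 to 1 ratio". It concludes: "We plan to recruit 126 patients (63 in each arm"). Testing is two-sided: "2-sided p values will reported and the level of significance is set at p<0.05".

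Randomisation uses random blocks of 4 or 8 and mentions no stratification factor.

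Inclusion criterion 2 reads "Spontaneous labour (contraction >2:10 minutes and cervical dilatation" of at least 3 cm. No upper limit is given. The criterion defines spontaneous labour and does not say that the value is the one at oxytocin start. Dilatation at oxytocin start is not listed among the recorded variables. The section on intrapartum care mentions "vaginal assessment for progress", but as monitoring during labour and not as a baseline measurement.

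**The concern.** The outcome clock starts at whatever dilatation a woman has reached when the infusion begins. A woman at 3 cm has, on the face of it, more labour ahead of her than a woman at 7 cm, whichever solution she receives. The protocol's background section itself describes labour duration by dilatation range, with slower progress between 4 and 6 cm in obese women. Variation in the interval that comes from starting dilatation has nothing to do with allocation, yet an unadjusted test leaves all of it in the error term.

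Two things are at stake. The confidence interval for the treatment difference is wider than it need be, and power is lower than the same 126 women could give. Also, if the arms happen to differ in starting dilatation, the unadjusted estimate carries that difference, and an adjustment added after seeing the imbalance would be open to challenge. If the value is not recorded before allocation, no later analysis plan can recover it.

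**Working it through.** **Inputs from the protocol (Sample size, Data Analysis):** difference 2 h, SD 4 h, two-sided alpha 0.05, power 80%, 1:1 allocation, 63 per arm.

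**Input not in the protocol:** R², the share of within-arm variance in the interval explained by dilatation. It is assumed here over 4 to 30%.

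**Step 1. Reproduce the stated sample size.** n per arm = 2 × (1.960 + 0.842)² × SD² / difference² = 2 × 7.849 × 16 / 4 = 62.8, rounded up to 63, total 126. This agrees with the protocol. Power at 63 per arm is 80.1% by the normal approximation and 79.5% by the exact t distribution. The exact figure is used below.

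**Step 2. Effect of adjustment.** In a linear model with arm and dilatation:
- residual SD = 4 × √(1 − R²)
- standard error of the difference = residual SD × √(2/63)
- 95% CI half-width = 1.96 × standard error
- unadjusted total with the same precision = 126 / (1 − R²)

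| R² (assumed) | Residual SD, h | SE, h | 95% CI half-width, h | Power for 2 h | Equivalent unadjusted total |
|---|---|---|---|---|---|
| 0 (as planned) | 4.00 | 0.713 | 1.40 | 79.5% | 126 |
| 0.04 | 3.92 | 0.698 | 1.37 | 81.1% | 131 |
| 0.10 | 3.79 | 0.676 | 1.32 | 83.5% | 140 |
| 0.20 | 3.58 | 0.637 | 1.25 | 87.6% | 158 |
| 0.30 | 3.35 | 0.596 | 1.17 | 91.4% | 180 |

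The degree of freedom spent on the covariate changes these powers by no more than about 0.01 of a percentage point.

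**Step 3. What R² might be.** This is an illustration only. Suppose dilatation at entry is spread evenly over 3 to 6 cm, or over 3 to 8 cm, and each extra centimetre means 1 h less labour. The SD of dilatation is then 3/√12 = 0.87 cm or 5/√12 = 1.44 cm. The correlation is 0.87 × 1/4 = 0.22 or 1.44 × 1/4 = 0.36, so R² is about 0.05 or 0.13. Power would be about 81% or 85%. The slope and both spreads are assumptions.

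**The case against.** The strongest reply is that nothing here is wrong. Under randomisation the unadjusted t-test is valid and unbiased, its standard error already allows for chance imbalance in dilatation, and the trial is sized for exactly this test. That stands. A reader might infer from the open-ended entry criterion that the primary comparison is biased or the trial underpowered as designed. The documents do not support either reading.

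A second temptation is to call dilatation a strong driver of the interval, or the strongest baseline predictor. The protocol gives no correlation. At R² of 4% the gain is under 2 percentage points, and the spread of dilatation among the women who will actually be augmented is unknown. This also stands, and it is why the range starts low.

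Nor can it be said that the sample size has no margin at all. SD 4 h was set above the cited 3.3 to 3.7 h, at which unadjusted power for 2 h would be 92% and 85%.

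It would also be too much to say that eligibility guarantees the needed value. Criterion 2 is not tied to oxytocin start, and the eligibility form is not shown.

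Finally, covariate choice is often left to an analysis plan. That carries less weight here, because the protocol itself names unadjusted tests and bases its sample size on one of them. What is proposed is a better choice than the one stated, not a missing detail.

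**Conclusion.** The point holds as one of efficiency. Starting dilatation is handled neither in the randomisation nor in the analysis, although entry is open from 3 cm upward and the outcome is time remaining to birth. The gain from adjusting runs from about 81% power (R² 4%) to about 91% (R² 30%), against 79.5% as planned, and the half-width of the 95% interval falls from 1.40 h to between 1.37 and 1.17 h. These figures rest on the protocol's 2 h and SD 4 h and on an assumed R². They also assume a roughly linear relation between dilatation and the interval. The direction is clinically plausible, but the size is not known from the documents. The change is worth making because it costs so little, not because the present plan fails.

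**What to change.** 1. Record cervical dilatation (cm) at the last examination before oxytocin start, with the time of that examination, before the numbered box is allocated. Add it to the listed baseline variables.
2. Make the primary analysis a linear model of the interval in hours on arm and dilatation. Report the adjusted mean difference with its 95% confidence interval.
3. State in advance what happens if the interval is skewed, since the current text would switch to Mann-Whitney U and lose the adjustment. Keep the same adjusted model, either with robust or bootstrap standard errors or on the log scale, and choose one before unblinding.
4. Keep the unadjusted comparison as supportive, and keep the sample size at 126.

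The cost is one recorded field, one degree of freedom and a few lines of text. SPSS, which the protocol already names, fits such a model. The downside is that the gain may be small if dilatation turns out to predict the interval only weakly.
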